## 16.1.9 Documentation of Statistical Methods

Receptos, Inc.  
Protocol RPC01-201

Statistical Analysis Plan – Part A, V1.2  
Date Issued: May 20, 2014

## 16.1.9 Documentation of Statistical Methods

Receptos, Inc.  
Protocol RPC01-201Statistical Analysis Plan – Part A, V1.2  
Date Issued: May 20, 2014**List of Abbreviations**

Abbreviation or Specialized Term	Definition
AE	adverse event
ALT	alanine aminotransferase
ANCOVA	analysis of covariance
ARR	annualized relapse rate
AST	aspartate aminotransferase
CI	confidence interval
CNS	central nervous system
CRF	case report form
C-SSRS	Columbia- Suicide Severity Rating Scale
DBP	diastolic blood pressure
DLCO	Diffusing capacity of the lung for carbon monoxide
ECG	Electrocardiogram
eCRF	electronic case report form
EDSS	Expanded Disability Status Scale
FDA	Food and Drug Administration
FEV 1	forced expiratory volume at 1 second
FS	Functional System
FVC	forced vital capacity
GCP	Good Clinical Practice
GdE	gadolinium enhancing
GGT	gamma glutamyltransferase
GLP	Good Laboratory Practice
HBsAg	Hepatitis B surface antigen
HBcAg	Hepatitis B core antigen
HCV	Hepatitis C virus
hCG	Human chorionic gonadotrophin
HDL	high-density lipoprotein
HIV	Human Immunodeficiency virus
ICH	International Conference on Harmonisation
IFN	interferon
IFN β-1a	interferon beta-1a
Ig	Immunoglobulin
IM	Intramuscular(ly)
ITT	intent-to-treat
IV	intravenous(ly)
IVIg	intravenous immune globulin
IVRS	Interactive Voice Response System
LCLA	low-contrast letter acuity
LFT	liver function test
LOCF	last observation carried forward

## 16.1.9 Documentation of Statistical Methods

Receptos, Inc.  
Protocol RPC01-201Statistical Analysis Plan – Part A, V1.2  
Date Issued: May 20, 2014

MCH	mean corpuscular hemoglobin
MCHC	mean corpuscular hemoglobin concentration
MCV	mean corpuscular volume
MSFC	Multiple Sclerosis Functional Composite
MRI	magnetic resonance imaging
MS	multiple sclerosis
MSQOL-54	Multiple Sclerosis Quality of Life-54
OCT	optical coherence tomography
PD	pharmacodynamic(s)
PFT	pulmonary function testing
PK	pharmacokinetic(s)
PP	per protocol
RBC	red blood cell
RPR	rapid plasma reagin
RMS	relapsing multiple sclerosis
S1P1R	sphingosine 1-phosphate 1 receptors
SAE	serious adverse event
SAP	statistical analysis plan
SBP	systolic blood pressure
SGOT	serum glutamic oxaloacetic transaminase
SGPT	serum glutamic pyruvic transaminase
TB	Tuberculosis
ULN	upper limit of normal
VZV	Varicella Zoster virus
WBC	white blood cell

## 16.1.9 Documentation of Statistical Methods

Receptos, Inc.  
Protocol RPC01-201

Statistical Analysis Plan – Part A, V1.2  
Date Issued: May 20, 2014

### 1 Administrative Structure

This study is being conducted under the sponsorship of Receptos, Inc. The clinical monitoring, data management and statistical analysis are being performed under contract with [REDACTED], in collaboration with Receptos, Inc.

#### 1.1 Data Quality Assurance

The Clinical, Data Management, and Biostatistics departments at [REDACTED] will work diligently and collaboratively, internally and with the sponsor, to ensure that the data collected and analyzed for this study are of the highest quality possible. This will be accomplished in part by having thorough edit checks written, programmed, and updated as needed to guarantee high quality data. Edit checks will be reviewed by the statistician, programmer and other team members on an ongoing basis to evaluate whether any checks need to be added or any existing checks need to be modified.

All analyses will be conducted using SAS Version 9.1 or higher.

### 2 Introduction

RPC01-201 is a phase 2/3 clinical trial consisting of a placebo-controlled (Part A, Phase 2) and active comparator trial (Part B, Phase 3) versus IFN  $\beta$ -1a [REDACTED] in patients with relapsing multiple sclerosis (RMS). Part A is a randomized, double-blind comparison of RPC1063 to a placebo control in patients with RMS to characterize the short-term efficacy and safety of RMS in improving disease activity as measured by MRI parameters. Part B characterizes the efficacy and safety profile of RPC1063 on longer-term clinical outcomes (e.g., relapse rate and disability progression) in RMS patients.

This statistical analysis plan (SAP) describes the statistical methods to be used during the reporting and analysis of clinical data collected in Part A of the study. This plan should be read in conjunction with the study protocol and the case report forms (CRFs).

Analyses of data collected during the optional extension of Part A, as well as analysis of data collected during Part B of the study will be described in separate SAPs. A separate analysis plan will also be developed to guide analyses of population pharmacokinetic (PK) data and a separate analysis plan will be developed to guide analyses of heart rate data collected from the Holter monitors.

### 3 Objectives

The primary objective of Part A is:

- To demonstrate the superior efficacy of RPC1063 compared to placebo by showing a reduction in the cumulative number of total gadolinium enhancing (GdE) lesions from Week 12 to Week 24 in patients with RMS

The secondary objectives of Part A are:

### 16.1.9 Documentation of Statistical Methods

Receptos, Inc.  
Protocol RPC01-201

Statistical Analysis Plan – Part A, V1.2  
Date Issued: May 20, 2014

- To assess the proportion of patients who are free of GdE lesions at Week 24
- To assess the effect of RPC1063 on the cumulative number of new/enlarging T2 lesions from Week 12 to Week 24
- To compare the clinical efficacy of RPC1063 to placebo in patients with RMS as assessed by reduction in annualized relapse rate (ARR) and proportion of relapse free patients at Week 24
- To assess the safety and tolerability of RPC1063 in patients with RMS
- To assess the pharmacokinetics (PK) and pharmacodynamics (PD) of RPC1063 in patients with RMS

The exploratory objectives of Part A are:

## 4 Investigational Plan

### 4.1 Overall Study Design and Plan

This is a multi-center, randomized, double-blind, placebo-controlled (Part A) and double-blind, double-dummy, active-controlled (Part B) parallel group study ([Figure 1](#)) to evaluate the efficacy and safety of RPC1063 administered orally to patients with RMS.

In Part A of the study, two doses of RPC1063 will be administered daily for 24 weeks with an efficacy and safety comparison to a placebo control. Approximately 210 patients who meet eligibility criteria as assessed during the 30-day screening period will be randomly assigned 1:1:1 to receive one of the three following regimens, up to Week 24:

- Placebo oral capsule daily
- RPC1063 0.5 mg oral capsule daily
- RPC1063 1 mg oral capsule daily

Patients who complete the 24 week placebo-controlled treatment period will have the option of entering a 24-week blinded extension period (Weeks 25 to 48). Patients assigned to either RPC1063 treatment group during the double-blind placebo-controlled period will continue in their respective treatment groups during the blinded extension; patients assigned to the placebo treatment group will be randomly assigned in a 1:1 fashion to one of the two RPC1063 treatment groups for the blinded extension.

## 16.1.9 Documentation of Statistical Methods

[figure not shown]
Receptos, Inc.  
Protocol RPC01-201Statistical Analysis Plan – Part A, V1.2  
Date Issued: May 20, 2014

Part A will be followed by Part B of the study, where two doses of RPC1063 will be administered daily for a 24 month period compared to an active control, IFN  $\beta$ -1a. Approximately 1200 patients who meet eligibility criteria as assessed during the 30-day screening period will be randomly assigned 1:1:1 to receive one of the three following regimens for 24 months:

- IFN  $\beta$ -1a 30  $\mu$ g intramuscular (IM) weekly
- RPC1063 0.5 mg oral capsule daily
- RPC1063 1 mg oral capsule daily

An interim analysis of Part A will be completed approximately 1 month prior to completion of Part A enrollment. Part B will commence after a DMC reviews the interim analysis data and performs a thorough safety review. Patients dosed in Part A will be ineligible for participation in Part B.

**Figure 1. Study Schematic**

#### 4.2 Study Endpoints

The primary efficacy endpoint of Part A is:

- Total number of GdE lesions, assessed on brain MRIs from Week 12 to Week 24

The key secondary efficacy endpoints (rank ordered) of Part A are:

- The number of GdE lesions at Week 24
- Total number of new or enlarging hyperintense T2-weighted brain MRI lesions from Week 12 to Week 24
- ARR at the end of Week 24

### 16.1.9 Documentation of Statistical Methods

Receptos, Inc.  
Protocol RPC01-201

Statistical Analysis Plan – Part A, V1.2  
Date Issued: May 20, 2014

The secondary safety endpoints of Part A are:

- AEs
- Laboratory evaluations
- Vital sign measurements
- ECG results
- Continuous Holter monitoring
- Physical and neurological examination
- OCT
- Pulmonary function tests
- Dermatological examination
- Columbia-Suicide Severity Rating Scale (C-SSRS)

The secondary PK and PD endpoints of Part A are:

- Standard PK parameters
- CBC with differential
- Plasma protein biomarkers (e.g., cytokines, chemokines, other inflammatory proteins)
- Total immunoglobulins (Igs) - IgA, IgG, IgM

Note: PK data from this study may be integrated with PK data from other clinical trials to further enhance a population PK analysis. Population PK analyses will be described under a separate analysis plan and documented in a separate pharmacometric report.

The exploratory endpoints of Part A are:

## 5 General Statistical Considerations

Statistical testing for the primary efficacy endpoint will be made between each of the RPC1063 treatment groups and placebo in Part A. A sequential testing procedure will be used to control the overall Type I error rate due to multiple comparisons. If the first comparison (RPC1063 1 mg versus placebo) is statistically significant ( $p \leq 0.04944$ ), then the second comparison (RPC1063 0.5 mg versus placebo) will be tested at the 0.04944 significance level. However, if the first comparison is not statistically significant, then the

## 16.1.9 Documentation of Statistical Methods

Receptos, Inc.  
Protocol RPC01-201

Statistical Analysis Plan – Part A, V1.2  
Date Issued: May 20, 2014

Provided that the primary comparisons are statistically significant, the sequential testing procedure will continue to be used for the secondary endpoints. The prespecified order includes both the order of the secondary endpoints and dose groups. Specifically, for each of the secondary endpoints, a sequential testing procedure will be used to control the overall Type I error rate due to multiple comparisons with the first comparison (RPC1063 1 mg versus placebo) and the second comparison (RPC1063 0.5 mg versus placebo). Secondary endpoints have been rank prioritized in the order shown in [Section 8.2](#) of the protocol.

Unless specified otherwise, all statistical analyses will be performed using a two-sided hypothesis test at the overall 5% level of significance. Accordingly, p-values will be rounded to three decimal places. If a p-value is less than 0.001, it will be reported as “<0.001”. If a p-value is greater than 0.999, it will be reported as “>0.999”.

Continuous data will be presented using descriptive statistics: n, mean, standard deviation, median, minimum and maximum. Categorical data will be summarized by the number and percent. Confidence intervals (CIs) will be 95% and two-sided, unless otherwise stated. Data will be displayed in all listings sorted by treatment group and subject number. When count data are presented, the percent will be suppressed when the count is zero in order to draw attention to the non-zero counts. A row denoted “Missing” will be included in count tabulations where necessary to account for dropouts and missing values. The denominator for all percents will be the number of subjects in that treatment within the population of interest, unless otherwise stated. Non-zero percentages will be rounded to one decimal place, except 100% will be displayed without any decimal places. Additional rounding rules are as follows:

- If the original value has 0 decimal places: mean, median, and CIs will have one decimal place and SD will have 2 decimal places
- If the original value has 1 decimal place: mean, median, and CIs will have 2 decimal places and SD will have 3 decimal places
- If the original value has 2 or more decimal places: mean, median, CIs, and SD will all have 3 decimal places

Minimum and maximum will always have the same decimal places as the original measure, up to a maximum of 3 decimal places.

Subgroup analysis will be performed for the primary and secondary efficacy endpoints where applicable. The following are the pre-defined subgroups:

- baseline EDSS score (EDSS  $\leq$  3.5 versus EDSS  $>$  3.5)
- baseline presence of GdE lesions (lesions present versus lesions absent)
- age at baseline (age  $\leq$  40 versus age  $>$  40)
- sex (female versus male)
- weight (<median versus  $\geq$ median)

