10.2.2. Day 5 Visit

This visit will be performed for safety purposes. Patients will be instructed that they must take the Day 5 study drug dose at the clinic before 12:00 pm (noon), after the Holter monitor has been placed. The following assessments will be performed at the Day 5 visit for the first 75 randomized patients:

- Observation of patients predose and for the first 6 hours following dose administration, including hourly vital sign monitoring
- ECG predose and at Hour 6
- Continuous Holter monitoring 15 minutes predose and for 24 hours following dose administration

If clinically significant cardiac conduction abnormalities are not observed in the first 75 patients that are treated, Day 5 monitoring will be discontinued for the remaining patients enrolled in the study. After that time, the first-dose monitoring strategy should be repeated at Day 5 if any

cardiac safety issues were observed at Day 1. If any safety issues are identified during Day 5 monitoring, then the monitoring guidelines in [Section 10.2.1.1](#) should be followed.

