### 5.1 Sample Size

The primary analysis of Part A will compare the cumulative number of new GdE lesions at the end of Week 24 in each of the RPC1063 groups to the placebo group using a 2-sided Wilcoxon-Mann-Whitney test. For this type of nonparametric analysis, the parameter of interest for sample size/power considerations is the probability that a randomly selected patient in an active treatment arm will have fewer lesions than a randomly selected patient in the placebo arm. Limited data are available from which to estimate this parameter. Based on the use of patient-level data from Tubridy et al. (1999) and Miller et al. (2003), estimates of this probability range from 0.634 to 0.754. Using the approach of Noether (1987), a sample size of 59 patients per group will provide 80% power to detect a difference if the true value of this probability is equal to 0.65 (Noether, 1987). Assuming a dropout rate of 15%, the planned enrollment is 210 patients (70 patients per arm).

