#### 5.3.3 Safety Population

The Safety population will include all subjects who have received at least one dose of study drug. All enrolled subjects will be assumed to have taken study drug unless otherwise confirmed. If it is confirmed that a patient never took a dose of study drug, then the patient will be excluded from all safety analysis. All subjects in the Safety population will be analyzed according to the highest dose of RPC1063 treatment actually received and not according to the treatment they are randomized to receive, in the event there is a discrepancy.

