## 10 Safety Analysis

All analysis of safety will be conducted using the Safety population. Statistical hypothesis testing will not be performed on any safety results.

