## 16.1.9 Documentation of Statistical Methods

Receptos, Inc.  
Protocol RPC01-201

Statistical Analysis Plan – Part A, V1.2  
Date Issued: May 20, 2014

The incidence of subjects with abnormalities in Liver Function Tests (SGPT/ALT, SGOT/AST, and GGT) will be summarized overall and at each visit for each treatment group for the following categories:

- $\geq 1 \times$  upper limit of normal (ULN)
- $\geq 2 \times$  ULN
- $\geq 3 \times$  ULN
- $\geq 4 \times$  ULN
- $\geq 5 \times$  ULN

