## 10.3 Vital Sign Measurements

Vital signs including standing and supine systolic blood pressure (SBP), standing and supine diastolic blood pressure (DBP), body temperature, and heart rate (HR) will be recorded on the eCRF once per visit at Screening, Week 4, Week 8, Week 12, Week 16, Week 20, and Week 24. In addition, pre-dose and hourly cardiac monitoring (blood pressures and heart rates) for hours 1-6 will be recorded for all patients at the baseline visit and for the first 75 patients on Days 5 and 8.

Summary tables including actual values and change from baseline (defined as pre-dose on Day 1) values will be presented for vital signs including SBP (supine and standing), DBP (supine and standing), temperature, and HR by treatment group for the Safety population. On Day 1, hourly changes from pre-dose in blood pressures and heart rates will be shown for all patients. For all other visits starting at Week 4, only a single timepoint will be collected and shown.

For patients participating in cardiac monitoring on Days 5 and 8, a summary table will be provided that summarizes the hourly change from pre-dose assessment through hour 6 at each of the baseline, Day 5, and Day 8 visits by treatment group for heart rate and blood pressure.

Box plots will be provided to display the distribution of vital signs. In addition, line plots will be created to display the change from baseline over the entire study period and change from pre-dose in vital signs for the baseline, Day 5, and Day 8 visits.

The number and percentage of subjects with SBP  $> 180$  mmHG or  $< 90$  mmHG and HR  $< 40$  beats per minute will be summarized by visit for each treatment group. The number and percentage of subjects with clinically relevant abnormalities will be presented by treatment group. The criteria for clinically relevant abnormalities are shown in the following table. Vital signs will be presented by subject in listings.

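### By-visit safety percentages use all treated patients in the arm as denominator, so patients not assessed at a visit count as event-free and the percentages are too low

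*SAP*

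**What the plan says.** SAP Section 5 (General Statistical Considerations) gives the default for every percentage: "The denominator for all percents will be the number of subjects in that treatment within the population of interest, unless otherwise stated". It also provides a row for missing data, which "will be included in count tabulations where necessary to account for dropouts and missing values".

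For safety, SAP Section 10 states: "All analysis of safety will be conducted using the Safety population". SAP 5.3.3 defines that population: "The Safety population will include all subjects who have received at least one dose of study drug".

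Two by-visit incidence summaries fall under this default:

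- **SAP 10.2.2 (Blood Chemistry).** Patients reaching successive multiples of the upper limit of normal for ALT, AST and GGT "will be summarized overall and at each visit for each treatment group for the following categories".
- **SAP 10.3 (Vital Sign Measurements).** Counts and percentages with systolic pressure above 180 or below 90 mmHg and heart rate below 40 "beats per minute will be summarized by visit for each treatment group".

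Neither section names a denominator. Protocol 10.2.2 restricts Day 5 cardiac monitoring: "The following assessments will be performed at the Day 5 visit for the first 75 randomized patients". SAP 10.3 likewise limits hourly blood pressure and heart rate on Days 5 and 8 to the first 75 patients.

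**The concern.** The SAP names a denominator where it wants something specific: randomized subjects for disposition (Section 6), the Safety population for medical history (7.2.1), dosed subjects for compliance (8.2.2). Silence in 10.2.2 and 10.3 therefore means that the Section 5 default governs. This is a stated rule, not a gap.

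Under that rule a patient with no reading at a visit adds nothing to the numerator but stays in the denominator. The missing-data row shows how many such patients there are; it does not change the percentage printed for the outlier category.

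At stake is the description of liver-enzyme elevation over time and, if Day 5 is tabulated, of blood pressure and heart rate during titration. Because the fraction assessed changes from visit to visit, an unchanged rate among those assessed would appear to fall wherever fewer patients are assessed.

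**Working it through.** **Inputs.** Part A plans 210 patients, 70 per arm, from 59 per group and 15% dropout (SAP 5.1). Allocation is 1:1:1 (SAP 5.2). The first 75 patients are monitored on Day 5 (Protocol 10.2.2 and Table 5; SAP 10.3). I assume that all 210 are dosed.

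**Reproducing the plan's figure.** Noether's formula with P = 0.65, equal groups, two-sided 0.05 and 80% power:

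N = (1.960 + 0.842)² / (12 × 0.25 × 0.15²) = 116.3 in total, or 58.1 per group, rounded up to 59.

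At the 0.04944 level N = 116.7, or 58.3 per group, again 59. Inflating for dropout gives 59 / 0.85 = 69.4, rounded up to 70 per arm and 210 in all. The stated figures reproduce.

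**Dilution factor** = default denominator / number assessed at the visit.

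- **Week 24.** If every planned dropout is unassessed, the factor is 70/59 = 1.19, so the printed percentage is 59/70 = 0.84 of the rate among those assessed. Earlier visits, with fewer losses, lie closer to 1.
- **Day 5, if tabulated and if monitoring stops at 75.** The factor is 210/75 = 2.80 overall, and 70/25 = 2.80 per arm if the 75 split evenly.

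**Illustration for Day 5.** If 2 of 25 assessed patients in an arm had systolic pressure below 90 mmHg, the rate among those assessed is 2/25 = 8.0%, but the rule prints 2/70 = 2.9%. On Day 1 all patients are monitored, so the same 8.0% would print as about 8.0%. The apparent fall of 1 − 1/2.8 = 64% between the two visits would be produced by the denominator alone.

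**Uncertainty in the 2.8.**

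- If the first 75 were a simple random draw from 210, one arm would contribute 19 to 31 of them (95% range), for a factor of 70/19 = 3.7 down to 70/31 = 2.3. The blocked randomization in SAP 5.2 should narrow this.
- Protocol 10.2.2 has Day 5 monitoring repeated in later patients who had cardiac issues on Day 1. The documents do not say how many. Assuming 5 to 20, the factor is 210/80 = 2.6 down to 210/95 = 2.2.

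**Liver tests.** Protocol Table 1 schedules clinical laboratory tests at screening, Day 1 and Weeks 4, 12 and 24, with none on Day 5. Only the dropout factor applies to them.

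**The case against.** The best case against the point is that the SAP keeps titration monitoring apart and that a reader can undo the dilution.

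- **Day 5 may not be in the outlier table.** SAP 10.3 lists screening and Weeks 4 to 24 as the visits with one vital-signs record, adds Days 5 and 8 separately, and gives the monitored patients their own table. This stands in part. That table shows hourly change from pre-dose and has no percentages, and the SAP does not list the outlier table's visits. Reading by-visit to include Day 5 is literal but not certain.
- **The cap of 75 is conditional.** Under Protocol Table 1, footnote 1, monitoring stops only if those 75 patients show no clinically significant slowing of heart rate or conduction problem. Several patients with heart rate below 40 could well mean that monitoring continues, and the shortfall would shrink or vanish. This stands, and is why the illustration above uses blood pressure.
- **Assessed-only rates are not the truth either.** Protocol 9.4.4.1 and 12.4 provide for discontinuation after a confirmed ALT or AST above 5 times the upper limit, so later assessed patients are partly selected on the outcome. This stands and shapes the fix.
- **Other outputs cover the signal.** Day 1 hourly changes are shown for all patients, bradycardia is an adverse event of special interest, vital signs are listed by subject, and Holter heart rate has its own plan. Counts and the missing-data row let a reader recover the number assessed. Table shells, promised in Protocol 13.3, might specify denominators, but they are not among the documents. All this limits the harm without making the printed percentage right.

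A reader might also infer a between-arm bias. With 25% against 5% dropout, for example, equal rates among those assessed would print 21% lower in the first arm (0.75/0.95 = 0.79). The documents give one overall dropout rate of 15% and no basis for such a difference. On Day 5, 1:1:1 allocation makes the dilution equal across arms in expectation.

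**Conclusion.** The point holds as a defect in descriptive safety reporting. Under SAP 5, the by-visit percentages in 10.2.2 and 10.3 treat unassessed patients as event-free and are lower than the rates among those assessed.

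The size is up to about 1.2-fold at Week 24, assuming that all planned dropouts are unassessed. It is about 2.8-fold on Day 5 under two conditions that the SAP does not settle: that the outlier table includes Day 5, and that monitoring stops at 75. It would be a mistake to read 2.8 as a general or certain factor, or to apply it to liver tests. The documents also do not support calling the assessed-only rate the true incidence.

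The damage is mainly to absolute incidence and to comparisons between visits. No safety hypothesis is tested and the primary analysis is untouched, so this should be corrected but does not threaten the trial's main conclusion.

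**What to change.** Amend SAP 5, 10.2 and 10.3 as follows:

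- For any percentage reported by visit, use as denominator the number of subjects in the arm with a non-missing assessment of that parameter at that visit, and print that number.
- List the visits included in the vital-sign outlier table.
- For Day 5, and for any Day 8 percentages, use the cohort scheduled for monitoring under the protocol. Report separately the patients monitored again because of Day 1 cardiac issues; they are selected on a cardiac finding and would distort the Day 5 rate. Day 8 needs a check first: SAP 10.3 expects vital signs then, while Protocol 10.2.3 and Table 5 list only Holter monitoring.
- Keep the full Safety population for overall incidence at any time after baseline, and show it beside the by-visit rates, since those condition on remaining in the study.

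The cost is a few sentences in the SAP and a small programming change. The one downside is that denominators vary by visit, which is why they must be printed.
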